#### Secondary outcomes

- 1. Length of hospitalization determined from hospital records, and a follow up call 7 days post-discharge.
- 2. Final diagnosis determined from hospital records.
- 3. 7-day post-discharge mortality status determined from a follow up call 7 days post-discharge.
- 4. 7-day readmission status determined from a follow up call 7 days post-discharge.
  - a. Facility of readmission.
  - b. Treatment received during readmission.

#### Participant involvement

Total study participation time is estimated to be a maximum of 60 min per participant in both the baseline (phase I) and intervention (phase III) periods.

#### Participant involvement in phase I and phase III

Potential participants will be recruited by study nurses while they are waiting in line to be seen by the hospital triage nurses. Participants can anticipate study procedures (including consent, clinical examination, and interview) to take between 35 to 50 min. The study nurses will conduct study procedures in the triage waiting area, while the participant is waiting in line to be seen by the hospital triage nurses. If it is the participant's turn to be seen by the hospital triage nurses, study procedures will stop and there will be no interference or delays in accessing standard care. Participants will also engage in a short (10 min) follow up call 7-days post-discharge.

#### Additional procedures in phase III

In the intervention period, the hospital triage nurses will be conducting triage using the digital triage tool (which will include a digitized version of the triage guidelines in already place at the study hospitals). It is important to understand that the digital triage tool will NOT be replacing standard care, but rather it will be integrated into standard care to supplement and strengthen existing triage systems.

To reiterate, the study nurses will conduct the same study procedures (consent, clinical examination, and interview) in both the baseline (Phase I) and intervention (Phase III) periods. These procedures are conducted while the participants are waiting in line to be seen by the hospital triage nurses. The difference in Phase III is that the hospital triage nurses (that the participants are waiting in line to see) will be using the digital triage tool to triage participants.

## Sampling and recruitment Sample size

**Model development considerations** The sample size for model development is based on two components: the number of predictors expected in the final model (effect-ive variables), n, and the outcome event rate, I. We employ the typical minimum standard of 10 events per effective variable and calculate the sample size as  $N = (n \ x \ 10)/I$ . Based on our previous study at a Kenyan hospital [16], we estimate the admission rate as I = 12%, and thus, to allow for a model with 10 predictors we require a minimum sample of 833 children.

**Power to detect difference considerations** Based on an assumed pre-intervention rate of 27% of children who receive a bundle of care within 1 h, an assumed 20% relative increase due to the intervention, and an alpha of 0.05, an estimate of 750 children per group is needed for 80% power. The assumed pre-intervention rate is consistent with previous studies [19] and confirmed in our feasibility trial of the application and dashboard in Uganda.

**Selected sample size** Based on the uncertainty commonly present in these smaller sample sizes [20], the desire to include the possibly of modelling non-linearities in our models (using machine learning methods) and the clinical feasibility (large case load) we plan to target a larger sample of 4000 at each site, with a minimum sample size of 1000 participants enrolled in Phase I. Based on the activity at our selected sites this would require no more than a 60% recruitment rate during a sixmonth period.

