### **Power to Detect Difference Considerations**

We have estimated the proportion of children who currently receive a bundle of care within one hour in the pre-intervention group to be 27%, based on findings from previous studies [19] and confirmed in our feasibility trial of the application and dashboard in Uganda. We will need at least 750 children for each of the pre-intervention and post-intervention conditions, using an alpha of .05, at power of 80%, to detect a 20% decrease in the proportion of children who receive the bundle of care within one hour.

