#### **Outcomes** analysis

We will be conducting our primary analysis using a difference in differences method. For our primary analysis, a logistic regression model for receipt of bundle of care within 1 h will be fit including: 1) phase of study (pre vs. post PRST) and 2) group (intervention versus control) as independent dummy variables and 3) their interaction. The interaction term corresponds to the difference in log-odds between groups in baseline vs intervention and it's exponent as the ratio of odds ratios. We will summarise this difference by estimating the marginal effect (risk difference) of phase in both the control and intervention groups. The difference of these marginal effects is the so-called 'difference in difference' for a binary outcome [24]. Confidence intervals will be based on the delta-method, or bootstrapping, where appropriate. A similar approach will be used for binary secondary outcomes (mortality, readmission), or quantile regression for median time to bundle of care, a non-parametric outcome.

Subgroup analyses specified a priori include Ugandan vs. Kenyan intervention site, young infant (under 2 months old) vs. children under 5 vs. older children, and presentation during day-shift hours versus night-shift hours (if applicable). We will also perform subgroup analyses on each triage category (emergency, priority, queue); patients from the pre-intervention phase will be retroactively categorized into these subgroups for this analysis. These subgroup analyses will be conducted with the inclusion of a three-way interaction between said variable, phase, and group. Statistical significance will be based on a likelihood ratio test comparing models with and without this term. This three-way interaction term would represent potential interactions between different subgroups and our difference in odds ratio obtained in our primary analysis, and results will again be presented on the risk difference scale based on marginal effects. This method of subgroup analysis sometimes termed a difference in difference in differences method.

Although none are expected, if there are any time varying confounders identified during the study that differ between intervention and control (health system or policy changes, natural events, changes in patient populations etc.) they will be included in above models as sensitivity analyses.

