As we are continually collecting data regarding predictors for admission alongside the clinical team, there is the possibility that our research activities may interact with the efficiency of delivering the sepsis bundle of care. Although the possibility of such interaction is minimized by our use of dedicated research personnel who would not approach patients who are actively receiving clinical care, any such interactions could potentially limit the external validity of our study to non-researchcontrolled settings. Therefore, to assess this potential interaction, we will pause the collection of predictor data 1 month before and after implementation of the PRST program. This pause will also occur in the control group in order to replicate any bias caused by changes in our primary outcome attributable to the pause rather than the PRST program. To investigate the potential for this bias, we will treat the collection or non-collection of predictors as a dummy variable for subgroup analysis using the difference in difference in differences method described above.

All analyses will be conducted using R statistical software [25], and an alpha level of 0.05 will be considered statistically significant for all outcome analyses.

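### The published protocol's 750 per group for 80% power sizes a two-group comparison, not its difference-in-differences primary analysis, which has about 38% power at 750 per group-by-phase cell

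*Combined protocol and SAP*

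**What the plan says.** The point lies within the published protocol (June 2020). Its sample-size section, under power to detect a difference, starts from a 27% baseline rate of treatment within one hour, takes "an assumed 20% relative increase due to the intervention" as the effect to be detected, and sets alpha at 0.05. It concludes that "an estimate of 750 children per group is needed for 80% power". The next paragraph selects a larger target of 4,000 at each site, with at least 1,000 enrolled in Phase I. The reasons given are the uncertainty of small samples, the wish to model non-linearity, and case load.

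In its Outcomes analysis section the paper states: "We will be conducting our primary analysis using a difference in differences method". The model is logistic for treatment within one hour, with phase, group and their product, summarised as a difference between two risk differences. The section adds that "an alpha level of 0.05 will be considered statistically significant for all outcome analyses" but does not say whether tests are one- or two-sided.

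Protocol version 5.0 (October 2020), section 13, carries the same number and says what the groups are: "We will need at least 750 children for each of the pre-intervention and post-intervention conditions". No sample-size paragraph in either document mentions the interaction or gives numbers per period at the control site.

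**The concern.** A sample size based on one baseline rate and one post-intervention rate has two sources of sampling error. A difference-in-differences has four, because the control hospital's own before-after change is estimated and subtracted. With equal cells this almost doubles the variance, so 80% power for the first comparison cannot be carried over to the second.

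A reader who takes the 80% as the power of the primary analysis would treat 750 per cell as adequate for the targeted 5.4-point gain, when a result that is not statistically significant would be likely at that size even if the gain were real. Correcting the two-group number alone would not solve this, because that still leaves the interaction unsized.

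**Working it through.** **Inputs.** From the published protocol: 27% baseline; 20% relative increase, so 0.27 × 1.2 = 0.324 and a difference of 0.054; alpha 0.05; 80% power; 750 per group. Assumed because not stated: two-sided test, control rate 27% in both periods, independent children, and the split of enrolment over phases.

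Variance terms: 0.27 × 0.73 = 0.1971 and 0.324 × 0.676 = 0.2190.

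**1. The plan's own figure.** For two proportions with mean 0.297,

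n = [1.96 √(2 × 0.297 × 0.703) + 0.8416 √(0.1971 + 0.2190)]² / 0.054² = 1,123 per group.

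One-sided, n = 885. At 750 per group the power is Φ[(0.054 √750 − 1.96 × 0.6462) / 0.6451] = Φ(0.329) = 62.9% two-sided, or 74.0% one-sided. So 750 is not reproduced even for the comparison that it appears to size. The nearest variant uses the direction in version 5.0 ("to detect a 20% decrease in the proportion of children who receive the bundle of care within one hour"), one-sided, and needs 779. This is a separate error from the one here.

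**2. Difference-in-differences, equal cells of n.**

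Var = (3 × 0.1971 + 0.2190)/n = 0.8103/n, against 0.4161/n for two groups, a ratio of 1.95.

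At n = 750, SE = 0.0329 and power = Φ(0.054/0.0329 − 1.96) = Φ(−0.317) = 37.6%. A simulation of 200,000 runs also gave 37.6%. On the log-odds scale of the interaction term, power is 35.8%. One-sided, it is 49.9% (risk difference). At 1,123 per cell, the corrected two-group number, it is 52.0%.

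For 80% power, n = (1.96 + 0.8416)² × 0.8103 / 0.054² ≈ 2,180 per cell (about 2,310 on the log-odds scale).

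**3. Two intervention hospitals pooled against one control, m per hospital per phase.**

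Var = (0.1971 + 0.2190)/(2m) + 2 × 0.1971/m = 0.6023/m.

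At m = 750, SE = 0.0283 and power = 47.8%. For 80% power, m = 7.849 × 0.6023 / 0.054² ≈ 1,620 per hospital per phase.

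**4. The selected target, 4,000 per site, split 2,000 and 2,000 over the phases.**

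| Sites | SE | Power, risk difference | Power, log-odds |
|---|---|---|---|
| Two intervention, one control | 0.0174 | 87.5% | 85.0% |
| One intervention, one control | 0.0201 | 76.5% | 74.1% |

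**The case against.** The strongest reply is that 750 is not the size of the study. The protocol presents it as a calculated requirement and then selects 4,000 per site. With the published design of two experimental hospitals and one control, that target gives about 87.5% power for the interaction if it is met and split evenly. This stands, and it limits the finding. A reader might infer from 38% that the trial as planned is underpowered; the documents do not support that. What remains is that the target is not justified by the power of the interaction, its split over phases is not given, and the control cells are never sized. The only power statement is still the 80% at 750.

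Three further limits also stand.

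- A reader might take 1,000 as the guaranteed size of every cell and quote its power. It is a minimum for Phase I enrolment only and says nothing about Phase III.
- A reader might extend the point to version 5.0. Its section 17 plans a Marascuilo comparison with historical and contemporaneous controls, segmented regression and other methods, and no difference-in-differences. The mismatch is therefore internal to the published protocol.
- Low power would not make a null result empty. The published protocol plans confidence intervals for the contrast, and these could still exclude larger effects.

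Sidedness, control rate and allocation are unstated, so 38% is conditional on the assumptions. The one-sided value is about 50%, still well below 80%.

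**Conclusion.** The concern holds as a mismatch between the stated sample-size basis and the stated primary analysis in the published protocol. At 750 per group-by-phase cell the primary analysis has about 38% power for a rise from 27% to 32.4%. It has about 48% with two intervention hospitals and one control at 750 per hospital per phase, and about 50% for equal cells if one-sided. About 2,180 per cell, or about 1,620 per hospital per phase in the two-to-one layout, would give 80%. At the 4,000-per-site target the figures are about 87.5% (two to one) and about 77% (one to one), so the design may be adequate if the target is reached.

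These figures assume a two-sided 0.05 test unless noted, an unchanged control rate of 27%, independent children and, at the target, an even split over phases. Two features not counted here would lower the power: clustering by hospital, and the published restriction of the effectiveness outcome to emergency and priority cases, which makes the analysable number smaller than enrolment.

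This should be fixed as a restatement. It is not evidence that the trial needs more children.

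**What to change.** In the published protocol's power paragraph, replace the 750-for-80% statement with the power of the interaction at the selected size. State the number of intervention and control hospitals, the numbers per phase including the control, the sidedness and the assumed control rate. Possible text: with two intervention hospitals and one control, 2,000 children per hospital per phase, a control rate of 27% in both periods, a two-sided alpha of 0.05 and independent children, power is about 87.5% for a 5.4-point difference-in-differences; about 1,620 per hospital per phase give 80%. If only one hospital of each kind contributes, the figures are about 77% and 2,180.

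Alternatively, keep 750 but label it as sizing a simple pre-post comparison only, and give its power there as about 63% two-sided.

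Do not add difference-in-differences power to section 13 of version 5.0 unless its section 17 is first reconciled with the published Outcomes analysis on which analysis is primary.

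The cost is a rewritten paragraph and a decision on numbers per phase. The power quoted for 750 becomes less favourable. The restatement needs no extra patients.

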#### Sampling strategy

A systematic method for participant selection based on time cut-offs will be adopted to minimize sampling bias. The study nurses will be instructed to screen the first patient arriving after each time cut-off (i.e. first patient to arrive after every 30-min cut-off). If the patient is not eligible, the next patient arriving after the time cut-off will be selected, and so on. The interval between time cut-offs will reflect the time a study nurse spends with each participant (35–50 min) to maximize efficiency. When there is more than one study nurse on a given shift, the time intervals will be staggered.

## Methods: data collection, management, and analysis

#### Data collection

#### Predictors, hospital outcomes, 7-day follow-up calls

All study nurses will be trained and well versed on the standard operating procedures to facilitate standardization

of all measurements. Study nurses will collect data using a custom-built Android application on a Samsung Galaxy Tablet A8. The list of predictors to be collected include clinical signs and symptoms, demographic/sociodemographic data, and pregnancy/birth information (see Additional file 1). Similarly, designated study nurses will obtain hospital outcomes (see Additional file 1) from patient records and enter them into the application on the Samsung Galaxy Tablet. Study nurses will conduct 7-day follow up calls in accordance with the standard operating procedures and enter the data into the application on the Samsung Galaxy Tablet.

#### Time outcomes

Timing tracking will be automated using customised RFID (see RFID system section for details).

#### Usability testing data

Think Aloud transcriptions and observer checklists will be entered into a computer and uploaded to REDCap. The Triage Tool Training Questionnaire (Additional file 2) will be captured on paper and stored in a locked cabinet, in a locked room in our research spaces nearby the study sites.

#### Post-study healthcare worker satisfaction survey

After completion of Phase III of the study, healthcare workers that participated in the usability testing initiative will be invited to complete a Healthcare Worker Satisfaction Survey (Additional file 3). This will be used to generate a report that provides insight on the overall perception of health worker's experiences with the digital triage tool.

#### Data management

#### Data collection infrastructure

Study Nurses will collect data using a custom-built Android application, created using LambdaNative (lambdanative.org), the open-source cross-platform toolkit developed internally at BC Children's Hospital Research institute. All data entered into the mobile application is stored in an encrypted database using the encryption cipher Rabbit. Access to the tablet and application is secured by passwords; without using the application, the encrypted files are not readable. The Masimo iSpO2° Pulse Oximeter with Micro USB Connector will be used to collect pulse oximetry and heart rate (including 30 s of raw plethysmographic data) and the Masimo Caregiver™ non-contact thermometer will be used to measure core temperature. The data collection application also contains complex error checking specific to the survey questions such as date inconsistency checks and ensures only relevant data items are collected, by dynamically hiding redundant questions.

Due to the complex nature of a large multi-center study, data will be uploaded directly from the Android tablets to REDCap (Research Electronic Data Capture, https://projectredcap.org/). REDCap is a secure webbased application designed to support data capture for research studies and it has been used for over 300,000 projects, in over 100 countries, including prior studies in Uganda [13]. Encrypted data will be stored for less than 14 days after completion of data collection on the tablets. In Kenya, the data will be directly uploaded weekly (depending on internet availability) over a secured internet connection to KTWRP servers, where it will be stored. A deidentified copy will be sent to the central study server at the BC Children's Hospital Research institute where data will be checked for completeness and consistency with data definitions. In Uganda, the data will be sent to the central study server at the BC Children's Hospital Research Institute. After this upload, the data on the tablets will be deleted. Each subject will be given a unique number and all data will be connected to this unique number. Using REDCap limits the amount of paper-based data, further ensuring data integrity and safety. The uploaded data will be accessible to only study team members with secure access to the server.

Data collected during follow-up interviews conducted by phone or in person will also be collected electronically and shared in the same secured manner. Personal identifiers are required for the collection of admission data and follow-up data. The data collection application contains several forms. All identifiers are collected on a single form, separate from the other forms containing non-identifying information, and stored in a separate and restricted REDCap form. Access to identifiers will be limited to those requiring this data for follow-up (i.e. only study personnel involved in follow-up or data verification). No analysts, co-investigators or principal investigators not directly involved in the follow-up or data verification will have access to this data. Access to RED-Cap will require 2-way authentication: in addition to the normal password process, a secure code (sent via SMS to the user) will be required for access to this data.

Paper based data collection items include consent forms and research assistant field notes (which do not contain identifiers). These will be stored in a locked cabinet, in a locked at our research spaces next to each study site.

#### Health intervention infrastructure

The bundle of care during the intervention will include triage in the OPD using an additional custom Android web-app, running locally on the device with no required Internet connection. As with the data collection app, this application will be password protected and data will be stored encrypted on the device. Following each triage, the triage data will be sent to a local low-cost Unix server Soekris box based in a secure room at each site. Data will be sent through encrypted HTTPS requests to server-side PHP scripts, which insert it within MySQL tables.

The clinician dashboard that will be used to clinically manage all children in the OPD who have been triaged will be implemented as a password protected website accessible by registered medical staff on any computer or tablet on the local network. As with the triage app, this website runs completely locally, independent of an outside Internet connection and is not accessible from offsite. The dashboard is implemented using the Laravel (https://laravel.com), a PHP web framework, which queries the MySQL server tables securely. Personal identifiers will be collected in the triage app and sent to the server for display on the dashboard as is necessary for correct identification of patients, but such information will never leave the hospital site. As the study hospitals already have computers in their OPDs, use of the clinical dashboard will not be extra work for the hospital staff or interfere with other tasks.

#### Statistical analysis

#### Model development

The predictive model for severe infection and sepsis in children will be developed based on the need for hospital admission of 24 h or longer. To find the best performing, and most parsimonious model, a variety of model building techniques will be compared. These will include but are not limited to: stepwise regression based on Akaike's Information Criterion (AIC), penalized regression via elastic net, and random forest [21]. Models will be compared based on the area under the receiver operating curve, and the specificity achieved at high (80-90%) sensitivity thresholds. Models within 10% of the best performing model will be considered. Final model selection will depend on parsimony, availability of predictors across sites (based on resources, cost and feasibility of collection), discrimination and calibration. All model comparisons will take place within an internal validation resampling framework such as cross validation or bootstrapping. Risk thresholds to stratify participants into triage categories (emergency, priority, and queue) be selected based on sensitivity analysis and expert opinion. To account for geographical differences and disparities in disease prevalence (high malaria prevalence in Jinja, Uganda), we will use net reclassification improvement to optimize and re-calibrate (if required) the prediction model [22].

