# 17. Statistical Analysis

### **Model Development**

We will develop a logistic model that will predict severe infection and sepsis in children. Akaike's Information Criterion (AIC) will be used as a summary measure to select predictors for inclusion in the model. The final selection of a model will be judged on model parsimony, availability of the predictors (with respect to resources and cost), discrimination and calibration. Bootstrapping (with replacement) will be used for internal validation. Net Reclassification Index for external (Kenya) and geographical/high malaria prevalence (Jinja) will be used for validation of the prediction model. These cohorts will allow us to optimize and re-calibrate (if required) the prediction model. Appropriate triage risk threshold selected based on data, simulation and expert opinion. The final model will be integrated into an application for use on a mobile device and electronic dashboard.

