#### Additional Analyses due to the impact of COVID-19:

# Develop data driven prediction models for identifying vulnerable children with suspected sepsis that are robust during future COVID-19 surges and novel pandemics.

We will specifically look at the predictive performance of the model during this initial pandemic period (2-3 months) in comparison to following non-pandemic period. We will use traditional statistical modeling techniques (e.g. logistic regression) and data-driven algorithms (e.g. elastic net and random forest) to identify new predictors and calibrate existing predictors, exploring possible interactions between periods. We will validate the model using test sets that include both post-and during-pandemic data in order to ensure that any newly derived model performs consistently during both periods. Performance of prediction models will rely on area under receiver operating characteristics, and specificity corresponding to 80% sensitivity. Our goal is to develop a model for identifying those most at risk for sepsis that performs well despite changes in case mix of our cohort, even if this slightly degrades overall prediction performance. This will ensure that the final model will be more robust to future changes in case mix during future health crises.

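### Net reclassification improvement is given the cross-site recalibration and validation role, but it does not measure calibration, and no calibration statistic or recalibration method is named

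*Combined protocol and SAP*

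**What the plan says.** The two texts give NRI related but different roles.

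- **Published protocol, Statistical analysis, Model development.** To deal with geographical and prevalence differences: "we will use net reclassification improvement to optimize and re-calibrate (if required) the prediction model". Here NRI is the tool for recalibration.
- **Protocol v5.0, section 17, Model Development.** "Net Reclassification Index for external (Kenya) and geographical/high malaria prevalence (Jinja) will be used for validation of the prediction model". The next sentence reads "These cohorts will allow us to optimize and re-calibrate (if required) the prediction model". Here NRI serves validation, and recalibration is tied to the cohorts with no method stated.

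Both texts include calibration among the criteria for the final model. The published protocol lists "parsimony, availability of predictors across sites (based on resources, cost and feasibility of collection), discrimination and calibration". Neither text names a calibration statistic, plot or limit.

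The other named measures are discrimination measures. In the published protocol, "Models will be compared based on the area under the receiver operating curve, and the specificity achieved at high (80-90%) sensitivity thresholds". In the COVID-19 analyses of v5.0, "Performance of prediction models will rely on area under receiver operating characteristics, and specificity corresponding to 80% sensitivity".

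On cut-points, the published protocol says "Risk thresholds to stratify participants into triage categories (emergency, priority, and queue) be selected based on sensitivity analysis and expert opinion". Section 17 of v5.0 refers to data, simulation and expert opinion. Neither text gives a number, an NRI type (category-based or category-free) or a comparator model.

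**The concern.** Recalibration is needed when a model's absolute risks are wrong at a new site even though its ranking of children is sound. The documents' own volumes suggest that admission rates differ by site. AUC and specificity at a fixed sensitivity do not change when the intercept is wrong, or when the slope is wrong but still positive. NRI does change, but it counts moves across cut-points between two models and does not compare predicted with observed risk. It can therefore rise when calibration worsens and fall when calibration improves.

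The tool assigns emergency, priority or queue from predicted risk. If the cut-points are already fixed when the model is adjusted for a site, an adjustment steered by NRI could move children between categories with no gain in discrimination.

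**Working it through.** **The plan's own figure.** No number in the plan concerns NRI. The only model-development figure is the minimum sample, N = (10 predictors x 10 events)/0.12 = 833, which reproduces.

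**Inputs.** The event rate is 12% (published protocol, Sample size). Assumed, because the documents do not give them: true logit risk is normal with SD 1.2 or 1.5 (AUC about 0.78 or 0.83), and the cut-points are as shown below.

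**Formula.** NRI = [P(up | event) - P(down | event)] + [P(down | non-event) - P(up | non-event)], by numerical integration. The reference is the perfectly calibrated model.

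**1. Wrong intercept, same ranking (SD 1.2).** The mean logit is -2.471. Adding 0.9 to every logit raises mean predicted risk from 12% to 22%.

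| Cut-points | Events | Non-events | NRI |
|---|---|---|---|
| 0.2/0.4 | +0.585 | -0.351 | +0.23 |
| 0.1/0.3 | +0.487 | -0.473 | +0.01 |
| 0.05/0.2 | +0.356 | -0.493 | -0.14 |

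The miscalibration is the same in all three rows; only the cut-points differ.

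**2. Cut-points closer to the plan.** At 0.2 the calibrated model catches only 51% of admissions. The 80-90% sensitivity that the plan uses to compare models needs lower cut-offs of about 0.09 to 0.06 in this set-up. With upper cut-offs from 0.15 to 0.50, NRI for the inflated model runs from -0.16 to +0.04 (lower cut-off 0.09) and from -0.23 to +0.01 (lower cut-off 0.06). In this range NRI mostly penalises over-prediction.

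**3. Optimising on NRI at one cut-off t (SD 1.5).** NRI against a fixed reference is largest when sensitivity + specificity is largest. That occurs when the cut falls at a true risk equal to the event rate. The NRI-maximising intercept shift is therefore logit(t) - logit(0.12):

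- t = 0.30: -0.847 + 1.992 = +1.145; mean predicted risk 25%
- t = 0.12: shift 0; mean predicted risk 12%
- t = 0.06: -2.752 + 1.992 = -0.759 (unrounded logits); mean predicted risk 6.8%

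Only t = 0.12 returns the calibrated model. At 0.06, a plan-like sensitivity, the error is under-prediction.

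**4. A site example from the documents' volumes.** Crude admission ratios are 2,000/20,000 = 10% in Kenya and 5,000/(100 x 365) = 13.7% in Jinja, assuming a 365-day clinic year. Suppose the sites differ only in the intercept (SD 1.5). A Kenya-derived model used in Jinja then has observed/expected 1.37. Correct recalibration improves the Brier score from 0.0953 to 0.0929. The NRI of that correct step is -0.07 at cut-off 0.05, -0.01 at 0.10, +0.07 at 0.20 and +0.10 at 0.30.

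**5. Category-free NRI.** A uniform upward shift scores exactly 0 (events +1, non-events -1), so it is blind to an intercept error. Multiplying the logit by 1.5 around 12% worsens the Brier score from 0.0841 to 0.0892 yet scores +0.99 (SD 1.5).

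**The case against.** **The recalibration charge fits one text only.** This stands. Version 5.0, dated October 2020 and later than the June 2020 publication, ties recalibration to the cohorts. A reader might infer that both texts recalibrate by NRI, but v5.0 does not say so. Its gap is that no recalibration method is given and that validation rests on an index that does not assess calibration. The published sentence could also mean that NRI is used to check whether a recalibrated model classifies better. It does not say that an intercept is tuned until NRI peaks, so step 3 shows what a literal reading of optimising on NRI would do.

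**The plan does not ignore calibration.** This also stands. A reader might infer that it does, but calibration is a stated selection criterion in both texts. What is missing is a statistic, and in the published protocol that selection sits within internal resampling, not the cross-site step.

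**NRI does not generally favour inflated risks.** Correct. A reader shown only the +0.23 might think so, but that value comes from cut-points far from the sensitivities the plan has in view. At lower cut-offs NRI mostly penalises inflation. Tuning on NRI still misses calibration there, in the other direction.

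**Harm to children is not established.** If thresholds are set on the recalibrated model at each site, a uniform shift is absorbed and no child changes category. The documents do not settle the order. The tool also supplements the existing triage system, and every child is assessed by a provider whatever the triage status. The effect on categories is therefore conditional.

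**Conclusion.** The point holds as a specification fault in model development. In the published protocol, the rule for recalibrating across sites uses a measure that does not assess calibration. In v5.0, cross-site validation uses the same measure and recalibration has no method. No measure named for that step reliably shows a wrong intercept or slope.

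For the same miscalibrated model (mean predicted risk 22% against 12%), NRI ranges from about +0.23 to -0.23 over the cut-points tried. Maximising it at one cut-off gives mean predicted risk of about 25% or 7% instead of 12%. These sizes depend on the assumed normal logit, its SD and the cut-points. That the sign depends on the cut-points does not rest on one SD: the results go the same way at SDs of 1.0, 1.5 and 2.0.

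If thresholds are fixed before recalibration, children move between categories. In the 0.2/0.4 illustration, the emergency share rises from 4% to 17% and queue falls from 82% to 56%. The documents do not support reading this as an expected result of the trial or as a fault in the effectiveness analysis itself.

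**What to change.** **Published protocol, Model development.** Base recalibration on calibration-in-the-large and calibration slope, with a calibration plot, in each site cohort. Re-estimate the intercept first and then the slope if needed. State what finding triggers each step, and whether the triage thresholds are set before or after recalibration.

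**Protocol v5.0, section 17.** Use the same calibration measures for external and geographical validation, together with AUC and sensitivity and specificity at the chosen thresholds in each cohort. Add the recalibration method there.

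**NRI.** It need not be deleted. It may stay as a secondary description, with the comparator model named, cut-points stated in advance, and event and non-event components reported separately. It should not drive recalibration.

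**Cost.** Changes of wording in two sections and a little extra analysis on data already being collected. No change to sample size or procedures.
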